#### **Available Alternative Opportunities/Treatments**

Describe alternative treatments or opportunities that might be available to those who choose not to participate in the study, and which offer the subject equal or greater advantages. If applicable, this should include a discussion of the current standard of care treatment(s).

Not applicable

[Back to Top](#)

#### **Records, Privacy, and Confidentiality**

Specify where the data and/or specimens will be stored and how the researcher will ensure the privacy and confidentiality of both. Specify who will have access to the data/specimens and why they need access.

Describe how data will be managed after the study is complete:

- If data/specimens will be maintained, specify whether identifiers will be removed from the maintained information/material.
- If identifiers will not be removed, provide justification for retaining them and describe how you will protect confidentiality.
- If the data/specimens will be destroyed, verify that this will not violate [retention policies](#) and will adhere to applicable facility requirements.

If this study will use de-identified data from another source, describe what measures will be taken to ensure that subject identifiers are not given to the investigator.

If applicable, describe procedures for sharing data/specimens with collaborators not affiliated with UK.

For additional considerations:

[Return of Research Results or Incidental Research Findings](#)

[HIPAA policies](#)

[FERPA policies](#)

[Procedures for Transfer agreements](#)

[Information regarding multi-site studies](#)

[NIH Genomic Data Sharing \(GDS\) Policy](#)

[Digital Data](#)

For all CARE2HOPE components, we will conduct the interventions and gather data in private spaces that reduce the risk that others will overhear study activities.

Interviewer-administered surveys will be conducted using Questionnaire Development Software's CAPI program, respectively. This platform allow surveys to be programmed and data to be entered by interviewers using a touchscreen laptop. Data are automatically password protected and are uploaded to a Data Warehouse on the HIPAA-compliant server at the UK Center on Drug and Alcohol Research (storefront staff and Emory-based team members can VPN into this server). We will enter locator data and biological test results in a password protected database and store audio files and transcriptions of audio recordings on a secure, HIPAA-compliant server managed by the UK College of Public Health and Rollins Schools of Public Health at Emory University. Specifically, quantitative survey databases, biological testing databases, audio files, and transcriptions will be stored on both UK College of Public Health and Rollins School of Public Health servers. Each participant will receive a unique identifying number and all research data collection instruments will be identified by this number only. The master list matching identifiers to specific participants will be maintained in a

separate, double-password protected database on the secure HIPAA-compliant server at the UK College of Public Health and Rollins School of Public Health at Emory University. We will store handwritten notes recorded during the survey and signed consent forms in a locked filing cabinet in a locked office in the UK College of Public Health. Audio recorders will be wiped of audiofiles after data have been uploaded to the server; if participants mention specific people by name, we will delete this part of the recording prior to uploading it (unless it is a public figure); notetakers will not record names in their notes (except those of public officials). Participants will not be identified by name in analytic data files. Research data will be reported in aggregate form only. The study is protected by a federal Certificate of Confidentiality, which will protect the investigators from being forced to release any identifying data, even under a court order or a subpoena.

All staff will sign a confidentiality agreement, stating that they will not disclose information about participants to others outside the study team.

Data sharing with the University of Washington Data Harmonization Coordinating Center (DCC) and within the Rural Opioid Initiative (ROI) consortium: Data from Kentucky CARE2HOPE are required to be submitted to the University of Washington as part of the NIH-funded Rural Opioid Initiative (ROI) data harmonization project. The University of Washington Data Harmonization Coordinating Center will be harmonizing data across 8 ROI studies in order to create new, harmonized datasets to be used for analyses across the consortium. The University of Washington and other ROI grantees will perform data analyses on these data for peer-reviewed publication. University of Kentucky and Emory investigators for this grant may be included as authors on manuscripts using these data. The harmonized datasets will be provided to other ROI grantees as required for analysis and will be considered under the umbrella of mandated DCC activities.

Once data are at the DCC it will be harmonized with data from the other 7 NIH-funded ROI sites to create new, harmonized datasets to be used for analyses across the consortium. Both the University of Washington and other ROI grantees will perform analyses on harmonized data sets, but no third parties outside of the ROI will be given access to this harmonized data. Harmonized datasets will be built to specific project concept proposals (i.e. will contain only necessary and pertinent data elements), and all project proposals must be reviewed and approved by the ROI consortium's Publications Working Group before distribution of the customized dataset.

All data submitted to the DCC will be de-identified with the exception of zip code, city name, and county of residence. The consent form specifies that identifying data will not be shared with other researchers with the exception of zip code, city name, and county residence (What Else Do I Need To Know Section). The consent also specifies that data will be shared with the University of Washington Data Coordinating Center. Data will be uploaded to the ROI Upload Server through a web interface. Access to the interface is controlled by usernames and passwords. Access is assigned to individual, designated ROI study staff by the University of Washington DCC. Staff are associated with their own studies only, and each ROI study may upload and manage its own data but is not able to view data from other studies. The web page uses the HTTPS protocol to transfer ROI data files securely to the Upload Server. HTTPS transfers are encrypted using Transport Layer Security (TLS, the successor to SSL), protecting the data enroute to the server. The Upload Server is managed in accordance with the DCC's information security policies (<https://uwcircg.github.io/hipaa-policies>), and authorization for specific DCC staff is based on their project-related needs and responsibilities.

We will also submit transcriptions for audio-recorded interviews to the DCC using the same protocol for transferring files securely. A Certificate of Confidentiality has been obtained from the National Institute of Health which, under federal law, prohibits all data collected during the course of a study protocol from being used in any legal or criminal proceedings. Participants will receive a copy of the consent showing the Certificate provisions and safeguards.

All research data will be kept in locked file cabinets at the University of Kentucky College of Public Health in [name]. Each participant will receive a unique identifying number. All research data collection instruments will be identified by this number only. The master list matching identifiers to specific participants will be maintained in a double-password protected database on a server at the Center on Drug and Alcohol Research at the University of Kentucky. Research data will be reported in aggregate form only without names or identifying information.

During interview and survey administration, should any participant feel uncomfortable answering any question, he or she will be free to abstain from answering that question or any other question. Likewise, participants can end their participation in intervention activities (e.g., START-C2H goal setting, or HIV testing and counseling) at any time, or choose not to engage in any component of the intervention they wish.

All study staff will be trained in Human Subjects protocols and will have passed the appropriate Collaborative Institutional Training Initiative (CITI) exams on human subjects research. Research staff will not press participants to answer questions that seem to be distressing to them. During interview administration, should any participant feel uncomfortable answering any question, he or she will be free to abstain from answering that question or any other question. In addition, research staff will respond to participants who show or express psychological distress and/or suicidal or homicidal thoughts by following the procedure Distressed and Suicidal/Homicidal Participants that has been a standard operating procedure in previous NIDA-funded trials (e.g., R01 DA027068). To offset the risk of distress associated with the data collection, all participants who express an interest will be provided with an information sheet on local resources. The list of referral agencies will include mental health centers, substance abuse facilities and support groups, and counseling facilities. Participants will receive the name of the referral agency, location, telephone number, fee, if applicable, statement describing the agency and the work that they do. If participants wish, we will assist them to make contact with services; however, we will not disclose any information about participants to referral agencies. The consent document will also contain a statement informing participants that their name and contact information may be released without their consent to appropriate state authorities in instances that are required by state law (e.g., if they inform study staff that they are wanting to end their life or someone else's life, or are abusing a child). Furthermore, a Certificate of Confidentiality has been granted to this study automatically (see <https://grants.nih.gov/grants/guide/notice-files/NOT-OD-17-109.html>). Under the Certificate of Confidentiality, section 301(d) of the Public Health Service Act (42 U.S.C. 241(d)) prohibits all data collected during the course of a study protocol from being used in any legal or criminal proceedings. Participants will receive a copy of the NIH Notice NOT-OD-17-109 granting the Certificate of

Confidentiality if so requested.

All research staff on this project will attend an intensive training that covers topics including human subjects protection and issues that could arise during jail-based data collection. Prior to any member of the research staff initiating contact with research participants, they will also be trained in the following areas: 1) Understanding the project grant (background, application, and aims); 2) Demonstrated understanding of all interview data collection forms; 3) Understanding how all forms are filed, both electronic and material (i.e. exact location, computer drive, folders, and which electronic files need to be password protected); 4) Understanding which type of events need to be reported and the process of reporting (e.g., emotional reports related to incidence of victimization or violence, adverse events reporting, exclusions after consent was obtained, cases of child abuse, active suicidal/homicidal ideation, releasing information, etc.); 5) Jail security training and familiarity with the environment (scheduling interview rooms, general etiquette); and 6) Interview and follow-up retention techniques (building participant rapport, tracking via weekly letters and phone calls, flexibility of interview times, dates, and locations, etc.). Training tasks will be organized by a checklist which will be completed during orientation. Staff will also complete training by the Kentucky Department of Corrections that covers codes of conduct for people visiting/working in correctional facilities and provides training on personal safety and on the importance of ensuring that all materials brought into the jail are also taken out of the jail by the interviewers (e.g., pens, study materials, etc.). Consistent with other studies led by Co-Is [name] and [name] involving justice-based populations, a two-day training session for REHNs (study interventionists) is proposed, in addition to on-going supervision for quality control to assure consistent delivery of services. The training approach will follow the procedures outlined by Carroll & Nuro (2002) which incorporates the following session content: 1) Overview; 2) Discussion of issues, including re-entry service coordination approaches; 3) Intervention goals and targeted behavior; 4) Discussion of similar approaches; 5) Specifications for intervention session content; and 6) Format for delivery and structure. Weekly clinical supervision will be provided by [name] and will focus on general clinical issues as well as intervention adherence issues. Individual sessions will be reviewed for adherence to the approach and will highlight fidelity.

REHNs will attend Project START trainings, offered through the CDC, to ensure that they understand how to ethically implement the intervention with fidelity to the original design.

REHNs will attend an HIV certification program offered by the Kentucky Cabinet for Health and Family Services to become certified HIV counselors. In addition, all staff will attend an in-house training sessions at the UK Center on Drug and Alcohol Research hosted by the PI ([name]) on how to use the INSTI and SureCheck HIV 1/2 Test specimen collection kits, and OraQuick® HCV Rapid Antibody Test. Staff will undergo training on how to respond to participants who show or express psychological distress and/or suicidal or homicidal thoughts. In addition, all study staff will undergo training on how to respond to participants who show or express psychological distress and/or suicidal or homicidal thoughts (e.g., facilitated by board certified psychiatrist, Co-I [name]). The procedure will follow the protocol for Distressed and Suicidal/Homicidal Participants that has been a standard operating procedure in previous NIDA-funded trials (e.g., R01 DA027068).

People who test negative will be provided with an information sheet on local resources. The list of referral agencies will include mental health centers, substance abuse facilities and support groups, and counseling facilities. Participants will receive the name of the referral agency, location, telephone number, fee, if applicable, statement describing the agency and the work that they do. If participants wish, we will assist them to make contact with services; however, we will not disclose any information about participants to referral agencies. The consent document will also contain a statement informing participants that their name and contact information may be released without their consent to appropriate state authorities in instances that are required by state law (e.g., if they inform study staff that they are wanting to end their life or someone else's life, are abusing a child).

Participants who test positive for HIV will be referred to their district Ryan [name] Part B HIV care coordinator. To maximize linkage to care, research staff performing testing will offer to call a Patient Services Coordinator at the UK Bluegrass Care Clinic (BCC; the HIV clinic serving Appalachian Kentucky) to set up an intake appointment on the participant's behalf while the participant is present. The BCC accepts all forms of private and public insurance and has grant funding to support services for uninsured patients. Participants who test positive for HCV will be referred to UK Kentucky Clinic Digestive Diseases and Nutrition [contact]) or St. Claire Regional Medical Center in Morehead, KY or encouraged to visit their primary care doctor for confirmatory (HCV RNA) testing.

Each individual will receive a unique identifying number and the screener form will be identified by this number only. The master list matching identifiers to specific participants will be maintained in a double-password protected database on the secure HIPAA-compliant server at the UK Center on Drug and Alcohol Research. Screener data will be reported in aggregate form only. Participants will not be identified by name in analytic data files. All electronic research data will be kept on the HIPAA-compliant server at the UK Center on Drug and Alcohol Research.

A Data Safety Monitoring Board will oversee the study.

**UK IRB policies** state that IRB-related research records must be retained for a minimum of 6 years after study closure. Do you confirm that you will retain all IRB-related records for a minimum of 6 years after study closure?

Yes  No

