At the group session, staff will provide a brief overview of the study, including describing the certificate of confidentiality and eligibility screening process. After the overview, participants will have the ability to ask the REHN questions. Following questions, the REHN will distribute paper copies of the screening survey (attached in Research Description) with a cover letter appended describing risks, benefits, and procedures involved in completing the screener (see Informed Consent section). The REHN will read the cover letter, screener instructions, and questions aloud to the group to support low-literate individuals. Individuals who consent will complete the screener. The screening survey will include questions to collect full name and date of birth so that staff can (1) accurately provide compensation on their commissary for completing the screening survey, (2) identify instances in which people complete the screening more than once so that they are not compensated for participation more than once, and (3) so that staff can extend invitations (via jail staff) to those who are eligible to meet with them to learn more about the study, go through the consent process, and complete a study intake.

The REHN will collect the screeners and thank the prospective participants for screening. Those that are eligible will work with the facility staff to determine a time and date that is convenient, and our staff person will meet them in a confidential room (i.e., the attorney-client room). Once with the participant, our staff will re-review the signed consent form to remind participants of what is involved and to make sure that they do indeed want to do their survey. If they do not want to participate, the research staff person will cancel the appointment without any consequences to the participant. Of note, the consent form is followed by a consent quiz to make sure that participants understand the procedures; one of the questions on the consent quiz asks if study participation will affect probation, parole, or release (true/false). If the participant fails the consent quiz, they will not be able to participate.

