
At the group sessions, staff will provide a brief overview of the study, including describing the certificate of confidentiality and eligibility screening process. After the overview, participants will have the ability to ask the REHN questions. Following questions, the REHN will distribute paper copies of the screening survey (see Screener Appendix in Data Collection section) with a cover letter appended describing risks, benefits, and procedures involved in completing the screener (see Informed Consent section). The REHN will read the cover letter, screener instructions, and questions aloud to the group to support low-literate individuals. Individuals who consent will complete the screener. The screening survey will include questions to collect full name and date of birth so that staff can extend invitations (via jail staff) to those who are eligible to meet with them to learn more about the study, go through the consent process, and complete a study intake.

The REHN will collect the screeners, thank the prospective participants for screening, remind them that those who are eligible will be contacted later in the day to schedule a one-on-one appointment with the staff person to review the consent form, discuss the study, and if consent is granted, complete the intake process for the study (described below).

For individuals who participate in the screening session, who meet all eligibility criteria except "be incarcerated in a local jail and expected to be released in <21 days" but are interested in participating in the study, we will obtain their permission to contact them again closer to their release date to see if they are still interested in the study. If permission is provided, the REHN assigned to the local jail will work closely with the jailer regarding the individual's release date and to arrange a time to meet with the potential participant again. The REHN will confirm the individual is still interested in the study; if so, the screening form will be completed again, ensuring the individual meets the eligibility criteria. If all criteria are met, the REHN will review the consent form, discuss the study, and if consent is granted, complete the intake process for the study.

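### The confidentiality section says the screener carries a study number only, but the paper screener used in jail group sessions itself collects full name and date of birth

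*Combined protocol and SAP*

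**What the plan says.** Three places describe how the screener is identified.

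- **Records, Privacy, and Confidentiality:** each person is given a unique number, and "the screener form will be identified by this number only". The same paragraph continues: "The master list matching identifiers to specific participants will be maintained in a double-password protected database". The name and the number are thus meant to meet only in a protected electronic list.
- **Prisoners form, Section 2, Condition 3(a):** at the jail group session "the REHN will distribute paper copies of the screening survey". Of that survey it says: "The screening survey will include questions to collect full name and date of birth". Three purposes are given: paying the screening compensation to the commissary account, detecting people who screen more than once, and inviting eligible people (through jail staff) to a one-on-one meeting.
- **Subject Recruitment Methods & Advertising, START-C2H Recruitment:** this repeats that the survey collects full name and date of birth, giving only the invitation purpose. It also sets the scene: "The REHN will read the cover letter, screener instructions, and questions aloud to the group to support low-literate individuals".

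Data Collection & Research Materials says that the screening survey determines eligibility. Under Study Population, people entering through the existing CARE2HOPE survey cohort qualify by membership. Everyone else recruited in jail must have used opioids to get high, or injected any drug, in the 30 days before incarceration.

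**The concern.** A form that asks for name and date of birth is not identified by a number only. If the procedure is followed as written, the protection promised in the confidentiality section does not apply to the paper screener while it carries both the identifiers and the answers.

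The form is sensitive because of what it has to establish and where it is filled in. Completion takes place in a group session inside the jail. The private attorney-client room is promised only for activities after a person screens eligible. Screening also comes before the signed one-on-one consent and rests on an unsigned cover letter. People found ineligible have filled in the form too, although they have no further part in the trial.

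The plan itself treats disclosure as a main risk, both under Condition 2 of the Prisoners form and under Potential Risks & Benefits. Its own precautions point the same way. The Department of Corrections consent form is given to every attendee so that officials cannot tell who screened eligible. Participants may also decline a copy of the study consent form because it mentions drug use. A completed screener bearing a name would reveal more than either document.

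**Working it through.** No arithmetic applies: the point depends on no sample size, effect or error rate. The check sets the descriptions of the screener side by side.

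| Question | Answer in the documents | Where |
|---|---|---|
| What identifies the form? | A unique number only | Records, Privacy, and Confidentiality |
| Where is the name linked to the number? | Double-password protected master list | Records, Privacy, and Confidentiality |
| What is the format in the jail group? | Paper copies, read aloud to the group | Condition 3(a); START-C2H Recruitment |
| Which identifiers does the survey ask for? | Full name and date of birth | Condition 3(a); START-C2H Recruitment |
| What is the survey for? | Determining eligibility | Data Collection & Research Materials |
| What must it establish outside the cohort route? | Opioid use to get high, or injection, in the 30 days before incarceration | Study Population |
| Is there a tear-off page, separate contact sheet or later redaction? | None described | No section |

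**Step 1: is the conflict real?** Rows 1 and 4 describe the same form and cannot both hold. The identifiers are deliberate, since Condition 3(a) gives three reasons for them. With row 7 empty, nothing in the text reconciles the two.

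**Step 2: does the form carry drug-use answers?** The screener is an attachment that is not reproduced, so this is an inference. It is a strong one: on the non-cohort route, a survey that determines eligibility has to ask about recent opioid use or injection. Where those items sit relative to the name is not known.

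**Step 3: do other safeguards close the gap?**

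- No hard-copy or electronic files are stored in the jail (Potential Risks & Benefits).
- Staff are trained that everything brought into the jail is taken out again (Records, Privacy, and Confidentiality).
- Completed paper screeners go into a lock box and then a locked cabinet. This is stated in the community recruitment text, not for the jail sessions.
- A cover letter is read aloud before screening and describes the risks and the Certificate of Confidentiality. No item captures information that would require mandated reporting (Informed Consent Process).

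Each of these lowers the chance or the consequence of disclosure. None separates the name from the answers, so none makes the number-only statement true.

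**Step 4: how many people does it reach?** The documents give no count of people screened on paper in jail groups. The enrolment figures (1,200 in Study Population; 12 counties × 20 participants = 240 in Statistical Design and Power) cover all routes and count enrolled people, not screened people. No number can be derived from them.

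**The case against.** The strongest reply is that the confidentiality paragraph concerns records once processed. Its neighbouring sentences deal with a server, aggregate reporting and analytic files, so it might mean that forms are labelled by number after they reach the office. That reading is possible, because the text does not say when the number takes over from the name. But the sentence speaks of the form itself, analytic files are covered in a separate sentence, and no step for removing the name is described.

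A second reply is that group paper screening is only one route. The COVID-19 text allows jail screening by Zoom or phone, with jail staff leaving the room before screening starts, and community recruitment adds online pre-screening. This stands as a limit on reach. It does not retire the group-session procedure, because the remote route is conditional on in-person meetings not being allowed.

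A third reply is that the safeguards were designed with this setting in mind. They were, and they make actual disclosure less likely.

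Three stronger readings are tempting and are not supported:

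- **That name and drug-use answers stand next to each other on the page.** The layout cannot be seen.
- **That screened people have no confidentiality protection.** The safeguards listed above apply.
- **That every collected form is an exposed form.** A form discloses something only if it is lost or seen, and the documents support no rate for that.

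Finally, this is not a threat to the trial's validity. It touches no allocation, outcome, power or analysis.

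**Conclusion.** The contradiction is explicit and needs correcting. The number-only statement is not true of the paper screener as the jail procedure is written. The consequence, that a completed form links a named inmate to illegal drug use, is very probable but rests on one assumption: that the unreproduced screener asks about the drug-use criterion it has to establish. The point covers everyone screened on paper in a jail group session, including those who prove ineligible, and its size cannot be put more exactly from the documents. It is a matter of participant protection that should be fixed because the remedy is cheap and changes what staff do. It gives no reason to doubt the trial's results.

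**What to change.** - Collect name and date of birth on a separate sheet that carries the study ID. Leave only the ID on the screener pages.
- Keep the identifier sheet physically apart from the screener from the moment of collection, and enter it in the protected master list. Until then the sheet is itself a paper link between name and number, so it should not travel with the screeners.
- Keep or destroy identifier sheets according to the retention policy; the plan cites a minimum of 6 years after closure for IRB-related records. Do so only after repeat-screening checks, any screening payment and any permitted re-contact are complete. Destroying them as soon as someone screens ineligible would conflict with START-C2H Recruitment, where people who fail only on release date may agree to be approached and screened again.
- Amend Condition 3(a), START-C2H Recruitment, and Records, Privacy, and Confidentiality so that all three describe this procedure. State the locked storage of paper screeners for the jail route as well.

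The separate sheet still serves all three purposes given for the identifiers. The cost is a reprint, one extra sheet to match by ID and a minor IRB modification.
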